7.7.4. Documenting AEs and SAEs

All adverse events, including SAEs that occur after dosing of study product must be documented in the Subject's medical records and on the CRF.

The Investigator should attempt to establish a diagnosis of the event based on signs, symptoms, and/or other clinical information. In such cases, the diagnosis should be documented as the AE and/or SAE term.

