6.2.1. Screening (Day 0)

The initial Screening assessment will be conducted the same day as the start of the Treatment Phase.

The following procedures/assessments will be performed at Screening:

- Informed consent (must be done prior to **any** of the following procedures)
- Eligibility review
- Medical history and Subject demographics (date of birth, gender, ethnic origin and race)
- Limited Physical Exam including NYHA Classification
- Composite Congestion Score (CCS)
- 5-point Current Dyspnea Score (using the script - [Appendix 7](#))
- Weight and height (Calculate BMI)
- Vital Signs
- % Lung Fluid Measurement (ReDS)
- Venous blood for clinical chemistries, hematology (run locally for eligibility), NT-proBNP (run locally for eligibility; 2nd sample sent to a centralized laboratory for subjects who qualify to participate)
- Urine pregnancy test on females of childbearing potential
- Administer the Kansas City Cardiomyopathy Questionnaire (KCCQ-12)
- Administer the patient global assessment visual analog scale (VAS)
- Administer Six Minute Walk Test (6MWT)
- Assess for adverse events
- Record concomitant medications (all medications taken within 48 hours)
- Schedule next study visit (Day 1).

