6.2.2. Treatment Phase (Day 0)

After the screening activities have been completed and laboratory analyses reviewed to confirm eligibility, the patient may be randomized (2:1) to receive either Furoscix or continued medical therapy with oral diuretics. Subjects randomized to continued medical therapy will follow the same schedule of assessments, excluding study product administration.

The initial dose of the study product should be administered after randomization. If randomized to Furoscix, product training with subject and/or caregiver will be conducted. The initial dose of the study product may be administered in the clinic or at home on the day of enrollment. Study staff will dispense additional doses of Furoscix. Subjects will be provided a Subject Diary in which to record any observed device issues and self-assessments that will be completed at home.

The Subject will be reminded to use the provided equipment to weigh themselves and record their blood pressure and heart rate and complete the patient global assessment VAS upon returning home and first thing in the morning on Day 1. They will also be reminded to bring their study product (device) and Subject Diary back to the clinic on Day 1.

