7. ADVERSE EVENTS

The Investigator is responsible for the detection and documentation of events meeting the definition of an AE or SAE as provided in this protocol. AEs will be assessed continuously

through the last study visit unless the nature of the AE or SAE requires continued monitoring. All AEs are recorded as mild, moderate or severe, and as Not Related, Possibly Related, Probably Related, or Definitely Related to the Investigational Product.

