7.1. Definition of an Adverse Event (AE)

An Adverse Event (AE) is any untoward medical occurrence associated with the use of an Investigational Product (IP) in humans, whether considered related to the IP. An adverse event (also referred to as an adverse experience) can therefore be any unfavorable and unintended sign (including an abnormal laboratory finding), symptom, or disease temporally associated with the use of an Investigational Product (IP) and does not imply any judgment about causality. An adverse event can arise with any use of the IP (e.g., off-label use, use in combination with another drug) and with any route of administration, formulation, or dose, including an overdose.

A “pre-existing” condition is one that is present prior to IP administration and is reported as part of the Subject’s medical history. Pre-existing conditions should be reported as AEs only if the frequency, intensity, or character of the pre-existing condition worsens during the study.

Laboratory or functional test abnormalities generally are not considered AEs unless they are associated with clinical signs or symptoms or require medical intervention. A laboratory abnormality (e.g. a clinically significant change detected on clinical chemistry, hematology, urinalysis) or functional test abnormality (e.g. a clinically significant change detected on ECG, pulse oximetry, or spirometry) that is independent from a known underlying medical condition and that requires medical or surgical intervention, or leads to IP interruption or discontinuation, must be considered an AE.

All AEs judged to be clinically significant, including clinically significant laboratory results, ECG and functional test abnormalities, will be followed until resolution or return to baseline or until no further improvement is expected.

An AE **does** include any:

- Exacerbation of a pre-existing illness.
- Increase in frequency or intensity of a pre-existing episodic event or condition.
- Condition detected or diagnosed after study product placement and/or drug administration even though it may have been present prior to the start of the study.
- Continuous persistent disease or symptoms present at baseline that worsen following the start of the study.

An AE **does not** include a/an:

- Medical or surgical procedure (e.g., surgery, endoscopy, tooth extraction, transfusion); the condition that leads to the procedure is an AE.

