7.7.6. Follow-up of AEs and SAEs

All AEs and SAEs documented at a previous visit/contact that are designated as ongoing will be reviewed at subsequent visits/contacts. AEs and SAEs will be followed until the last study visit unless the nature of the AE or SAE requires continued monitoring. If a Subject dies during participation in the study or during a recognized follow-up period, a copy of any post-mortem findings, including histopathology, should be obtained, if available, and forwarded to scPharmaceuticals or designee. New or updated information will be recorded on the originally completed SAE Report Form with all changes electronically signed/dated by the Investigator or designee.

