7.7.7. Post-study AEs and SAEs

Should the Investigator learn of an AE or SAE occurring within 30 days after a Subject completes the study, the event should be reported if it is considered related to study product.

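### Protocol 7.7.4 and 7.7.3 tie AE documentation to dosing, which controls never have, and the SAP sets no onset window for the AE tables, so AE counts can differ by arm

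*Protocol*

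**What the plan says.** Incidence of AEs, AEs of special interest (AESIs) and SAEs is a primary endpoint (Protocol 3.2.1, SAP 10.1) and is to be described in each group (Protocol 8.4.1).

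Two sets of passages govern what is collected.

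- **Not tied to dosing.** Protocol Section 7 says "AEs will be assessed continuously", and the sentence runs on "through the last study visit unless the nature of the AE or SAE requires continued monitoring". It also has every AE recorded by severity and relatedness. The Screening list in 6.2.1 includes "Assess for adverse events", and each later contact list (6.2.3 to 6.2.11) has an equivalent item. Section 6.2.2 adds: "Subjects randomized to continued medical therapy will follow the same schedule of assessments, excluding study product administration". Section 7.7.6 says "AEs and SAEs will be followed until the last study visit".
- **Tied to the product.** Section 7.7.4 requires entry in the medical records and on the CRF of "All adverse events, including SAEs that occur after dosing of study product must be documented". The second sentence of 7.7.3 has abnormal findings assessed against AE criteria when they appear, or worsen, after the product is given. Section 7.1 opens its AE definition with "any untoward medical occurrence associated with the use of an Investigational Product (IP) in humans", and one bullet of its list of what counts as an AE refers to product placement or drug administration.

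After the study, 7.7.7 covers an AE or SAE that the investigator happens to learn of within 30 days of completion: "the event should be reported if it is considered related to study product".

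SAP 15.3.1 tabulates any AE, treatment-emergent AEs, SAEs and other categories. It states no earliest or latest onset date.

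**The concern.** Control subjects receive no study product, so a duty that starts at dosing has no start for them. For Furoscix subjects, the same sentence passes over events between consent and the first dose. The trial is open label, so staff applying a product-based rule know which arm the subject is in. At the other end, a post-study rule that depends on relatedness to the product can realistically be met only in the Furoscix arm.

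If a site took 7.7.4 as its working rule, or if post-study events went into the incidence tables, the Furoscix column would be more complete than the control column. The primary objective is pilot data on effectiveness and safety for a pivotal trial. Control AE rates that were too low, or a between-arm difference created by recording rules, would carry into that planning. Changing the analysis population later does not recover an event that was never entered.

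**Working it through.** The plan states no figure on this point, so there is none to reproduce. The check compares the passages and then does simple arithmetic on the arm sizes.

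**1. Start of recording.** Section 7 has no dosing condition. The visit lists start at Screening on Day 0, before randomization, and 6.2.2 gives controls the same schedule. Section 7.7.4 starts at dosing. For controls the two cannot be matched. For Furoscix subjects they differ by the interval from consent to first dose. The reference point in 7.7.3 has the same gap. That matters because all four AESIs (Protocol 3.2.3) are defined by laboratory values. SAP Section 9 also dates treatment-emergent AEs from the first study drug administration, a date controls do not have.

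**2. End of recording.** Section 7 and 7.7.6 end at the last study visit, Day 30 ± 5, in both arms. Section 7.7.7 then applies for 30 days, but only to product-related events and only if the investigator hears of them. AESIs are limited to 30 days (Protocol 3.2.3, SAP 10.3). SAP 15.3.1 sets no such limit for AEs and SAEs, and no passage says where post-study events are tabulated.

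**3. Weight of one subject.** SAP Section 4 gives 51 subjects at 2:1: 51 × 2/3 = 34 and 51 × 1/3 = 17. Assume controls are included in the tables.

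- One control whose only AE is not entered: 1/17 = 5.9 points off control incidence.
- One Furoscix subject whose only AE is a late related event: 1/34 = 2.9 points on Furoscix incidence.

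**4. Outer bounds, on assumed risks.** The documents give no AE risk. Assume the same true risk p in both arms.

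- *Section 7 and the visit lists are followed:* no in-study loss at any p.
- *Extreme opposite, no control AE is entered:* expected controls with an unrecorded AE = 17 × p, and the chance of a two-sided Fisher exact p < 0.05 (Furoscix count binomial with n = 34, control count 0) is as follows.

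| Assumed p | Controls with unrecorded AE | Chance of spurious p < 0.05 |
|---|---|---|
| 10% | 1.7 | 1.7% |
| 30% | 5.1 | 84% |
| 50% | 8.5 | about 100% |

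In that extreme, 8/34 against 0/17 already gives p = 0.040. The lower row of outcomes needs every site to disregard Section 7, so this is a bound and not an estimate.

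**The case against.** The strongest reply is that 7.7.4 is not the only recording rule. It says what must be documented and does not say that nothing else may be. Its dosing clause can be read as qualifying SAEs alone. Section 7 makes the investigator responsible for documenting AEs and has all of them recorded. Section 7.7.1 requires notification of all SAEs within 24 hours. Section 9.1.7 requires a CRF for every consented subject. The list in 7.1 includes worsening of existing illness with no product condition, and the mandatory sentence of 7.7.3 does not mention dosing. AESI thresholds are checked on blood drawn at clinic visits in both arms. Section 7.7.7 is a passive rule for the period after completion and does not contradict Section 7. AE incidence is described by group, and SAP 15.3 says only that group comparisons may be tested.

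Most of this stands, and it rules out three stronger readings that a reader might infer:

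- *Controls' AEs are exempt from CRF entry.* No passage says so, and several require the opposite.
- *AE capture does differ by arm and the safety comparison is biased.* Both arms share the same visit lists, so this is a risk under a literal reading and not an established fact.
- *Furoscix subjects have an AE window running to Day 65 (35 + 30).* Passive reporting of related events is not scheduled ascertainment, and the SAP does not say that these events enter the tables.

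The reply does not give 7.7.4 or the second sentence of 7.7.3 a meaning for controls. Reading the clause as applying to SAEs alone still ties SAE documentation to dosing. Nor does it supply the missing onset cutoff in SAP 15.3.1.

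**Conclusion.** The point holds as a minor inconsistency. Sections 7.7.4 and 7.7.3 use a trigger that does not exist in one arm and does not match Section 7 or the visit lists. The SAP leaves open whether post-study events, which can realistically arise only under Furoscix, are counted in tables for a primary endpoint. AE counts can therefore differ by arm.

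The size cannot be derived from the documents. It depends on which passage sites follow and on whether post-study events are tabulated. The per-subject weights also assume that controls are in the safety tables. Read literally, the Safety population (Protocol 8.2, SAP 14) requires a dose of the product and so excludes all 17 controls. That is the larger defect, and the two should be corrected together.

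**What to change.** 1. **Protocol 7.7.4.** Replace the dosing clause with: *that occur from informed consent through the Day 30 (± 5) visit, in both treatment groups*.
2. **Protocol 7.7.3, and the one bullet in 7.1 that refers to product placement or drug administration.** Use the start of the study, or randomization, as the reference for both arms. Leave the rest of 7.1 as it is, because some of its sentences properly concern use of the product.
3. **SAP 15.3.1.** Restrict the between-arm incidence tables to onset from randomization through the Day 30 (± 5) visit in both arms. A cutoff at exactly Day 30 would drop valid events from subjects seen on Days 31 to 35. Put pre-randomization events and 7.7.7 post-study events in separate listings.
4. **Safety population.** Correct the definition in the same revision.

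For items 1 to 3 the cost is protocol and SAP wording and a memo to sites. No visit or data source is added, because AEs are already asked about at each scheduled contact in both arms.

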7.7.5. Regulatory/Ethics reporting requirement

The Investigator must comply with the applicable local regulatory requirements related to the reporting of SAEs to the IRB.

7.7.6. Follow-up of AEs and SAEs

All AEs and SAEs documented at a previous visit/contact that are designated as ongoing will be reviewed at subsequent visits/contacts. AEs and SAEs will be followed until the last study visit unless the nature of the AE or SAE requires continued monitoring. If a Subject dies during participation in the study or during a recognized follow-up period, a copy of any post-mortem findings, including histopathology, should be obtained, if available, and forwarded to scPharmaceuticals or designee. New or updated information will be recorded on the originally completed SAE Report Form with all changes electronically signed/dated by the Investigator or designee.

7.7.7. Post-study AEs and SAEs

Should the Investigator learn of an AE or SAE occurring within 30 days after a Subject completes the study, the event should be reported if it is considered related to study product.

7.7.8. Medical Monitor

SAEs and other medical matters can be discussed with the Medical Monitor.

8. STATISTICS

8.1. General Statistical Issues

This is a multicenter, randomized, open label, controlled study evaluating the effectiveness and safety of the Furoscix Infusor vs. continued medical therapy in patients with chronic heart failure and fluid overload requiring augmentation in diuretic therapy outside of the acute care setting.

Unless otherwise specified, all safety data, effectiveness data, demographic data, and other baseline clinical characteristics will be summarized by treatment group. Continuous data will be summarized by reporting the number of observations, mean, standard deviation, minimum, median, and maximum values. Categorical data will be described using frequency tables showing the number and percentage of subjects falling within a particular category. Shift tables will be given where appropriate to show change compared to baseline values.

Statistical analysis tests will be performed at a two-sided alpha level of 0.05, unless otherwise specified. Between-group analyses of baseline characteristics will employ descriptive statistics as described in the SAP. Mortality and morbidity events will be assessed using appropriate statistical tests as described in the SAP. The primary endpoint will be measured using the Finkelstein-Schoenfeld Method, comparing components of the composite endpoint hierarchically, as described in the SAP. There will be no imputation of missing data.

8.2. Analysis Populations

- Intent-to-Treat (ITT): All randomized subjects.
- Safety: All randomized subjects who received at least one dose of the Investigational Product.
- Per-Protocol (PP): All randomized subjects who received at least one dose of the Investigational Product AND completed the Day 30 clinic visit assessments AND have a Day 7 NT-proBNP value available for analysis.

All effectiveness analyses, including the primary endpoint and baseline characteristics will be performed on the ITT and Per-Protocol populations as further defined in the SAP. Safety analyses will be performed on the safety population.

8.3. Baseline Characteristics and Subject Disposition

Subject disposition (e.g., the number of Subjects enrolled, completed, and discontinued overall and by reason) will be summarized using the categorical descriptive statistics described in §8.1 above. Overall baseline clinical and demographic data will be summarized using descriptive statistics and compared between treatments using appropriate statistical tests as defined in the SAP.

8.4. Effectiveness Analyses

The following endpoints will be assessed.

8.4.1. Primary Endpoints

The primary analysis compares the components of the primary composite endpoint hierarchically using the Finkelstein-Schoenfeld Method. Each patient is compared to all other patients with respect to each of the following endpoints at 30 days:

- CV death
- HF hospitalization
- Urgent ED/Clinic visit for worsening heart failure (defined as IV diuretics, augmentation of or new administration of metolazone)
- Change in NT-proBNP from baseline at Day 7.

Each endpoint will be descriptively presented as well.

Incidence of Adverse Events, Adverse Events of Special Interest, and Serious Adverse Events will be described in each group.

8.4.2. Secondary Endpoints

Descriptive and statistical comparisons of treatment vs. control group will be conducted for each secondary endpoint at a two-sided 0.05 level of significance. The following secondary endpoints will be compared between treatment groups on the ITT and Per-Protocol populations as described in SAP:

- Days alive and heart failure event-free (hospitalization for heart failure or ED visits for heart failure) over 30 days.
- Changes from baseline in patient global assessment via visual analog scale (VAS) across follow-up timepoints.
- Changes from baseline in composite congestion score across follow-up timepoints.
- Changes from baseline in 5-point Current Dyspnea Score across follow-up timepoints.
- 7-point Dyspnea Score across follow-up timepoints.
- Changes from baseline in health-related quality of life measured by the KCCQ-12 Short Form Summary Score across follow-up timepoints.
- Changes from baseline in serum creatinine across follow-up timepoints.
- Changes from baseline in ambulatory body weight across follow-up timepoints.
- Changes from baseline in Six-Minute Walk Test (6MWT) across follow-up timepoints.
- Changes from baseline in the ReDS Lung Fluid Measurement across follow-up time points.

8.5. Interim Analysis

There will be no formal interim analysis.

8.6. Safety Analyses

Safety analysis will be performed on the safety population. No imputation will be performed for missing data. The incidence (number and percentage of subjects) of adverse events will be presented overall and by MedDRA System Organ Class (SOC) and Preferred Term (PT) for each treatment group. This analysis will be repeated for serious adverse events, for treatment-related adverse events, adverse events of special interest and for adverse events leading to premature study withdrawal.

Descriptive statistics at each time point will be presented for laboratory variables, vital signs, and body weight, stratified by treatment group.

8.7. Subgroup Analysis

The primary endpoint will be compared between treatment groups within pre-specified subgroups defined in the SAP. There will be no formal treatment comparisons within subgroups. The purpose of the analysis within subgroups is not to show statistical significance between treatments within subgroups, but to assess the consistency of treatment effect across subgroups.

9. RESPONSIBILITIES

9.1. Investigator Responsibilities

9.1.1. Good Clinical Practice

The Investigator will ensure that this study is conducted in full compliance with the principles of the "Declaration of Helsinki" (as amended in Edinburgh, Tokyo, Venice, Hong Kong, and South Africa), ICH guidelines, or with the laws and regulations of the country in which the research is conducted, whichever affords the greater protection to the study Subject. For studies conducted under a United States IND, the Investigator will ensure that the basic principles of "Good Clinical Practice," as outlined in 21 CFR 312, subpart D, "Responsibilities of Sponsors and Investigators," 21 CFR, part 50, 1998, and 21 CFR, part 56, 1998, are adhered to.

9.1.2. Institutional Review Board (IRB)/Independent Ethics Committee (IEC) Approval

This protocol and any accompanying material to be provided to the Subject (such as advertisements, Subject information sheets, or descriptions of the study used to obtain informed consent) will be submitted, by the Investigator, to an IRB [or] EC. Approval from the IRB/EC must be obtained before starting the study and should be documented in a letter to the Investigator specifying the protocol number, protocol version, documents reviewed, and date on which the committee met and granted the approval.

Any modifications or amendment to the protocol must also be submitted to the IRB/EC for approval prior to implementation.

9.1.3. Informed Consent

It is the responsibility of the Investigator or designee to obtain written informed consent from each individual participating in this study after adequate explanation of the aims, methods, objectives, and potential hazards of the study and prior to undertaking any study-related procedures. The Investigator or designee must utilize an IRB-approved consent form for documenting written informed consent. Each informed consent will be appropriately signed and dated by the Subject and the person obtaining consent. A copy of the signed consent form will be provided to the Subject.

